In July of 2015, the CDC released the most updated statistical report on fetal and perinatal mortality. There were 23,595 documented fetal deaths in the year 2013, gestational age 20 weeks and greater. Minority and marginalized women are disproportionately affected; with black women comprising 26% and Hispanic women comprising 20% of the reported cases [34]. Our Bronx population includes these vulnerable populations, who stand to gain the most from evidence based protocols and improvements in the management of fetal demise. The community surrounding our Montefiore Weiler and Wakefield labor and delivery is identified as 45.3% Black and 58.4% Hispanic by US Census data [35]. Safely shortening the length of labor induction can greatly benefit the emotional and medical safety of our patients. A prolonged induction puts a woman at increased risk for: coagulopathy, sepsis, hemorrhage, and complications that require surgical intervention [22]. Mifepristone has a well-tested and known safety profile and has been proven to optimize the effects of misoprostol, which is the standard medication for induction of labor in the setting of fetal demise [6].

1.2 Hypothesis:

The addition of mifepristone, when compared to placebo, to the standard accepted methods of induction of labor will expedite time to delivery of the fetus in women with intra-uterine fetal demise at 20 weeks gestational age and greater.

1.3 Objectives:

1. To compare time to delivery of fetus after administration of mifepristone or placebo at the onset of labor induction.
2. To calculate the duration of induction and hospitalization time among the two groups including time to delivery of placenta, duration of time on labor and delivery, time as an inpatient, and number of nights in the hospital.
3. To determine the number of women, in each arm of the study, who require surgical interventions due to a failed induction or retained products of conception.

4. To determine if administration of mifepristone augments misoprostol, oxytocin and mechanical cervical dilation.
5. To explore the overall incidence of complications and their association with mifepristone use, such as febrile morbidity, infection requiring antibiotics, or transfusion.

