5. Control Arm: Ingest a placebo tab orally with similar physical properties. This will coincide with or be implemented prior to the initiation of the induction of labor plan as delineated by the attending physician. The timing will be sensitive to the needs of the participant and the labor and delivery room staff.
6. Montefiore protocol for induction of labor:
 - a. 12w0d-23w6d: Misoprostol 400 micrograms vaginally every 3 hours for 5 doses.
 - b. 24w0d-28w6d: Misoprostol 400micrograms vaginally every 6 hours for 5 doses.
 - c. 29w0d and older: Misoprostol 25-50mcg vaginally every 4 hours for 4 doses OR 100mcg vaginally every 12 hours for 4 doses.
 - d. Induction methods and protocols will be at the discretion of the physician team and tailored to the clinical context.
7. Data: Patient data will be collected by the Labor and Delivery staff via electronic medical record or paper record that will be scanned into the electronic medical record. The investigators will use data abstraction tools to collect information such as time of medication administration, medications administered, time of delivery of fetus, duration of admittance to labor and delivery, and postpartum course, or complications from the electronic medical record.

2.2 Definitions:

1. Intrauterine Demise: Absence of fetal heart motion on bedside ultrasound; confirmed by two separate providers and the attending physician.
2. Mifepristone: A 19-nor-steroid derivative of norethindrone that competitively binds to progesterone and glucocorticoid receptors, with antagonist effect. Mifepristone administration is the standard of care when providing medical management for first and second trimester terminations/abortions as per the American Congress of Obstetricians and Gynecologists.
3. Induction of Labor: The use of medications and other techniques to induce contractions and cervical change with the goal of effecting delivery and evacuation of all uterine contents.

2.3 Protocol Amendments:

All amendments to the protocol by the primary research team will be delineated on handouts and distributed at participating Labor and Delivery Units at 8AM the following day. The same information

will be electronically mailed to resident physicians, attending physicians, physician assistants and nurse managers currently staffing the participating Labor and Delivery units.

III Drug Information

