The hospital staff will maintain medical records as per standard of care. The research team will assign a unique numerical participant identifier with enrollment and allocation of participants. As previously mentioned this identifier will correspond with the information on the sealed medication envelope. Case report forms (CRF) will capture relevant data such as: medication administration time points, clinical events and secondary outcomes. Nursing, pharmacy and medical records will be reviewed to assure accuracy and completeness. Data proofing and collection will be completed by persons blinded to treatment assignment. Intake measures will include: age, socio-economic status, gestational age, method of attainment of gestational age, insurance, gravidity and parity, previous cesarean deliveries, medical history, most recent hemoglobin and hematocrit. Admission data will include cervical exam, membrane intact or rupture status, and vital signs. Secondary outcomes, additional interventions, and adverse events will be captured on the CRF. Due to the fact that participants will be inpatient for the duration of their induction and post-partum course, we do not anticipate any significant withdrawals, deviations or incomplete data sets. Patient identifiers will be secured in locked and protected environments. The CRF and abstracted data will not have any patient identifiers.

VII Statistical Guidelines

7.1 Sample Size:

Based on a review of the literature, institutional charts and clinician experience, the mean time to delivery of fetus is projected to be 24 hours with a standard deviation of 6 hours. To detect a change in 4 hours, with a two-sided alpha of 0.05 and power of 0.8: 37 persons would be needed in each group for a total of 74 persons enrolled in the study. The effect of 4-hour reduction is chosen because it is considered a clinically significant reduction.

7.2 Analysis:

An intention to treat analysis will be completed. Two sample t-test and Wilcoxon rank sum test will be calculated for the primary outcome of time to delivery of fetus. Other secondary outcomes will be described with descriptive statistics and compared with ANOVA or Chi square analysis.

VIII Ethical Consideration

8.1 Confidentiality:

The participants, providers, and research team will all be blinded for the duration of the study. The patients' medical information is protected under HIPAA, therefore only staff directly involved in the

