patients' care and the primary research team will access the participants' medical records. All personal identify information will be removed from CRF. A unique participant identifier will be utilized for all data collection and analysis. In a separate locked and secured location the consent forms will be secured with a log of participants enrolled in the research.

8.2 Dissemination Policy:

Data collected during the study by labor and delivery team is confidential and protected by HIPPA. Abstracted data without patient identifier will be entered into CRF. The data will then be analyzed and reported.

8.3 Declaration of Interest:

The investigatorshave nothing to declare. Our purpose is to enrich the current body of knowledge on induction of labor for an intrauterine fetal demise in the second and third trimester.

8.4 Potential Benefits:

If Mifepristone expedites the delivery of the demised fetus, women in the control of the arm of the study will benefit tremendously from participating in the study as their induction will be shorter. This outcome has important consequences as it will avoid secondary complications from long inductions such as maternal infections and surgery. Additionally, a quicker induction time may ameliorate the emotional suffering of the patients.

8.5 Adverse Event and Safety Monitoring Board:

A safety monitoring board will be identified consisting of two clinician scientists who are familiar with scope of clinical practice but are not directly involved in the research. These physicians will review adverse events and work closely with the principle investigator and research team to assure that safety and reporting standards are maintained at a high level. The principle investigator will also actively review all outcomes for the patients throughout the course of the study, and will remained blinded to their treatment. Data will be abstracted within 72 hours of enrollment from the electronic medical record onto case report forms for the majority of participants. Timing regarding abstraction of serious adverse events onto case report forms is delineated below. The PI will review all CRFs and cross check to the medical record for accuracy every 6 weeks. There will be quarterly communications between the PI and monitoring board regarding adverse events and a written annual reports of these communications will be compiled regarding the review and assessments by the monitoring board. The PI and research team will

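### Does Section 7.2 need a rule for women whose fetus is removed surgically after a failed induction?

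*Combined protocol and SAP*

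**What the plan says.** Section 7.2 commits to intention to treat and then states: "Two sample t-test and Wilcoxon rank sum test will be calculated for the primary outcome of time to delivery of fetus". Objective 1 in Section 1.3 gives the comparison as: "To compare time to delivery of fetus after administration of mifepristone or placebo at the onset of labor induction". Neither mentions the route of delivery.

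Surgery is foreseen elsewhere. Objective 3 counts the women in each arm "who require surgical interventions due to a failed induction or retained products of conception". Section 8.4 says of a shorter induction that "it will avoid secondary complications from long inductions such as maternal infections and surgery". Section 2.2, item 3, defines induction as treatment "with the goal of effecting delivery and evacuation of all uterine contents".

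The misoprostol schedules in Section 2.1, item 6, run from "Misoprostol 400 micrograms vaginally every 3 hours for 5 doses" to "100mcg vaginally every 12 hours for 4 doses", and item 6d adds: "Induction methods and protocols will be at the discretion of the physician team and tailored to the clinical context". Section 7.1 projects a mean of 24 h with SD 6 h, and powers the trial for a 4 h change with 37 women per group. Section VI expects no significant withdrawals or incomplete data, because women remain inpatients.

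**The concern.** A t-test and a rank test need one number per woman. A woman whose induction fails has no time of delivery by induction. She could be given the time of surgery, placed at the worst rank, or left out, and Section 7.2 does not choose. Intention to treat rules out leaving her out and keeps her in her arm, but gives her no value.

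The choice could matter. If mifepristone prevents failures, they gather in the placebo arm. An early operation would then score a failed induction as a quick delivery and shrink the apparent benefit, while a late one would enlarge it. The two planned tests could also disagree, and a rule chosen after unblinding could be chosen for its result.

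**Working it through.** **The plan's own figure.** Inputs from Section 7.1: difference 4 h, SD 6 h, two-sided alpha 0.05, power 0.80. The noncentrality is 4 / (6 × √(2/37)) = 2.867 on 72 degrees of freedom, which gives t-test power 0.808. At 36 per group power is 0.797. So 37 per group reproduces.

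**Assumptions.** Times are normal with SD 6 h and means 24 h (placebo) and 20 h (mifepristone). The documents give no failure rate and no time of surgery, so both are assumed below. Powers come from 20,000 simulated trials with 37 per arm. With no failures the difference is 4.0 h, with t-test power 81% and Wilcoxon 79%.

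**Case 1: the slowest 15% v 5% fail, and surgery at S hours counts as delivery.** The mean among non-failures is mu − 6 × phi(z)/(1 − p).
- Placebo: 24 − 6 × 0.2332/0.85 = 22.354 h.
- Mifepristone: 20 − 6 × 0.1031/0.95 = 19.349 h.
- Difference with failures counted at S: (0.85 × 22.354 + 0.15 S) − (0.95 × 19.349 + 0.05 S) = 0.62 + 0.10 S.

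| Surgery time | Difference | t-test power |
|---|---|---|
| 15-24 h (mean 19.5 h) | 2.57 h | 59% |
| 30 h | 3.62 h | 80% |
| 36 h | 4.22 h | 79% |
| 48 h | 5.42 h | 71% |

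The difference equals 4 h at S = (4 − 0.62)/0.10 = 33.8 h. Dropping failures would give 22.354 − 19.349 = 3.01 h, but that contradicts intention to treat.

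Every row of the table uses the same analysis rule. Only the assumed timing of surgery changes, so writing the rule into Section 7.2 would leave the whole 2.6 to 5.4 h spread in place.

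**Are the extremes plausible?** The slowest 15% and 5% are women whose modelled times exceed 30.2 h and 29.9 h. At 15 h, 93% of the placebo distribution is still undelivered, and at 24 h 50% is. Surgery at 15-24 h would therefore have to pick out exactly these women while many others continued. At the other end, these women's modelled mean times are 33.3 h and 32.4 h, so 48 h is about 15 h later. The 15 h (5 × 3 h) and 48 h (4 × 12 h) are course lengths from different gestational-age bands in Section 2.1. No text says surgery follows when the doses run out.

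**Case 2: all undelivered women have surgery at 30 h.** This cut-off produces failure rates close to 15% and 5% without selecting women by their future times. The mean is mu × Phi(z) − 6 × phi(z) + 30 × (1 − Phi(z)), with z = (30 − mu)/6.
- Placebo, z = 1: 24 × 0.8413 − 6 × 0.2420 + 30 × 0.1587 = 23.50 h; 15.9% fail.
- Mifepristone, z = 1.667: 20 × 0.9522 − 6 × 0.0995 + 30 × 0.0478 = 19.88 h; 4.8% fail.
- Difference 3.62 h; t-test power 80%, Wilcoxon 79%.

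A 24 h cut-off would give 2.5 h, but needs failure rates of 50% v 25%.

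**Case 3: rarer failures, the slowest again.** At 10% v 3% the difference is 1.555 + 0.07 S: 2.92 h at 19.5 h and 4.92 h at 48 h. At 3% v 1%, about one woman in 37 on placebo, it is 3.232 + 0.02 S: 3.62 h to 4.19 h, with t-test power 77% to 81%.

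**Cost of the obvious remedy.** Suppose the Wilcoxon test with failures tied at the worst rank became the sole primary test. In the 15/5% case its power is 78%. If failures are equal in both arms and unrelated to speed, it is about 69% at 5% per arm and 60% at 10%. The t-test with surgery counted at 15-24 h has 78% and 75% there, and with surgery counted at 48 h 52% and 36-37%.

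**The case for a change.** The best argument for a change compares two rules on the same data. With 15% v 5% failures and surgery at 15-24 h, Wilcoxon power is about 55% if surgery counts as delivery and 78% if failures are ranked worst. With surgery at 48 h, the two planned tests disagree on significance in 14% of trials, against 5% with no failures. Section 3.1 presents faster delivery as a surrogate for the morbidity of a protracted or failed induction, so scoring an early operation as a quick delivery sits badly with that rationale. A written rule would cost only a sentence or two.

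The omission stands, and so does the arithmetic. The inference to a needed change does not. The large contrast depends on assumed failure rates and on early surgery confined to women who would have been slowest. Objective 3 pools failed induction with retained products, and Section 8.4 says only surgery, so neither shows that surgical removal of the fetus is common. Surgery for retained products after the fetus is delivered leaves the primary time untouched.

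Worst rank is also a different estimand, not a repair. It gives up the hours scale on which the 4 h target is set, and it needs a definition of failed induction that the plan does not contain. It can cost or gain power depending on facts nobody has in advance. Statisticians would reasonably differ on it.

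**Conclusion.** No change to the plan follows. Section 7.2 leaves a handling convention unwritten, and the text points to a sensible one: delivery by any route, timed when it happens, with every randomised woman kept in her arm. The comparison is then valid under the null hypothesis, whatever the failure rate. Section V keeps the allocation scheme from the researchers until data collection is complete and also blinds the analysis team, so analysts can record the convention without seeing results by arm. A worst-rank analysis can be shown alongside it.

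The size is unknown from the documents. Under the plan's N(24, 6) and N(20, 6), surgery at a common 30 h moves the difference from 4.0 to 3.6 h and t-test power from 81% to 80%. At 3% v 1% failures the difference stays within 3.6 to 4.2 h. The conclusion rests on failures being uncommon, or on surgery not being concentrated very early or very late. If failures were near 15% v 5% with surgery at such extremes, the estimate would move materially, but mainly because of when surgery took place, which a sentence in Section 7.2 would not control.
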